## 8.1.2 Analysis of Time-to-Event Data

In the proposed cohort study, several time-to-event outcomes of potential interest are (1) ESRD, (2) transplantation, (3) the initiation of dialysis, (4) GFR falling below 15 ml/min|1.73m^2, and (5) a pre-specified reduction (say 50%) in GFR. The survival analysis methods described in this section apply with equal force to each of these endpoints of interest and represent an important component of the armamentarium to address the study aims.

The use of time-to-event methods in cohort studies requires considerable attention to the underlying assumptions and censoring mechanisms. One particular issue concerns the incompleteness of outcome data. Careful consideration should be given to the censoring strategy, since censoring at the last time individuals were seen could lead to biased estimates if cases are actively sought and collected up to the date of the analysis [Muñoz 1997]. For instance, were event ascertainment complete, it would be more appropriate to censor follow-up time at the date of analysis [Hoover 1993], rather than at the date last seen. For most studies, an appropriate censoring strategy will be somewhere between these two extremes (i.e., the last contact and the date of analysis). The optimal approach will depend on the study design developed by clinical investigators in concert with KIDMAC investigators. For the analysis of time-to-ESRD, the trajectories of censored observations can be used to estimate when an individual will reach the threshold that defines an event. In doing so, we will circumvent informative censoring since we will use internal data to complete the missing information of when an individual reaches the threshold that defines an event. The complementary use of methods for longitudinal data and survival analysis will be a subject of methodological research by KIDMAC investigators.

Analytical Methods using Time since CKD Diagnosis as the Time Scale. The most common time scale for the analysis of data from cohort studies is the time since entry into the study, with analysis typically carried out in strata determined by biomarkers of disease progression (e.g., GFR). However, this may not be the most appropriate timeline for analysis. A more natural approach is to consider the time axis as the duration of disease, incorporating the time from CKD onset until the date of the baseline visit as late entries to avoid survivorship bias. Under a Generalized Gamma (GG) distribution [Cox 2007], the likelihood function can easily accommodate the data incompleteness embodied in late entries and censored times. Due to the relatively long times since CKD diagnosis at study entry for many of the participants, we can restrict the analysis to the occurrence of RRT after 2 years from the CKD diagnosis. It will be important to continue to recruit children with glomerular disease, who are more likely to enter the study shortly after their diagnosis, and very young children with non-glomerular disease, who are most frequently diagnosed at birth in order to inform the early portion of the survival curve proximate to CKD diagnosis. The data to be collected

CKiD Protocol OSMB Approved by CKiD during the funding cycle of this renewal application will be conducive to obtaining a more complete picture of CKD progression, especially in the time interval immediately subsequent to CKD diagnosis.

Parametric survival methods may provide clinical insight about the underlying disease process. Semi-parametric methods are of limited use for the estimation of the rate of disease itself and for quantifying the effect of an exposure in terms of the contraction (or expansion) of the disease-free time that an exposure induces. To estimate such measures, we propose to use a variety of parametric approaches, such as modeling times using lognormal, Weibull, or Gamma distributions [Muñoz 1996b, Piantadosi 1995]. Parameters defining the shape of these distributions can be modeled as a function of covariates, and standard likelihood inferences and goodness-of-fit tests can be made. KIDMAC investigators have successfully applied parametric survival methods for the analysis of HIV/AIDS data and bronchial responsiveness [Muñoz 1996a, Muñoz 1996b]. Methodologically, the analysis of bronchial responsiveness has commonalities with the analysis of chronic kidney disease. Namely, the outcome of interest is the time a marker takes to reach a threshold. As discussed by [Muñoz 1996a], when the event is the crossing of a threshold by a marker, the degree by which the threshold is surpassed contains information for when in between two discrete visit dates the threshold would have been achieved had intermediate visits occurred. Such information is of use to calculate the actual but unobserved event time.

Treating competing risks appropriately may increase clinical understanding. Competing risks methods have been utilized in CKiD to investigate differences in progression to dialysis and transplant. Two major approaches to competing risks are the cause-specific hazards method, which partitions the total hazard as the sum of mutually exclusive cause-specific hazards [Putter 2007], and the sub-hazards method, which partitions the total cumulative incidence as the sum of mutually exclusive cause-specific cumulative incidence as the sum of mutually exclusive cause-specific cumulative incidences, each with its own underlying sub-hazard [Fine 1999]. A typical application of these methods involves a single binary covariate, such as baseline urine protein:creatinine ratio above or below 2, which divides the cohort into two groups and leads to the estimation of relative hazards. Often, regardless of the approach chosen, an assumption may lead to erroneous conclusions if violated. Specifically, if the sub-hazards for both events are assumed to be proportional, the two relative sub-hazards must lie on opposite sides of 1; but independent estimation methods do not account for this, and results may not adhere to this requirement.

The relative cause-specific hazards and relative sub-hazards are inextricably linked to the cause-specific cumulative incidences, and are therefore tethered. In particular, proportionality cannot simultaneously hold for all hazard types [Beyersmann 2012]. The simplest way to avoid incongruent results is to eschew the proportionality assumption and include time dependency in the model. This adjustment is easily implementable in software with competing risks packages such as STATA and R. Models free from the assumption of proportionality are more appropriate for the complexities of the associations between exposures and outcomes, and often provide a clearer depiction of

the time-dependent effects of exposures on the competing endpoints than simply estimating a time-averaged effect.

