Eligibility for Cohort 3 will be determined by having a Non-Glomerular diagnosis of CKD whose duration is less than 5 years at date of enrollment and age between 6 months to 16 years old. In order to assure that CKD is present, for specific non-glomerular diagnoses, we will require two or more of the following: 1) urine protein to creatinine ratio greater than 0.5 for children less than 2 years old, or urine protein to creatinine ratio greater than 0.2 for children 2 years of age and older; 2) hematuria (for at least 3 months): 3) evidence of renal tubular disorders; 4) abnormalities detected by kidney biopsy or imaging (bilateral disease or solitary kidney disease); 5) a serum creatinine measurement greater than 0.4mg/dL for children less than 2 years old, or, for children 2 years of age and older, an estimated Glomerular Filtration Rate (eGFR) less than 90 ml/min|1.73m^2 based on the updated Schwartz formula; or 6) hypertension defined by documented note in medical record, current treatment of hypertension, or blood pressure > 95th percentile on at least two occasions. Additionally, these conditions must have occurred after the initial 6 months of life (with the exception of abnormalities detected by kidney biopsy or imaging) and must not be secondary to a current or resolving episode of acute kidney injury. Since description of course to renal replacement therapy is of primary interest, children who are expected to receive renal replacement therapy within 6 months of date of enrollment will not be recruited. Eligible children must be willing to complete baseline and follow-up testing, and all procedures at scheduled annual visits for the duration of the study. Spanish-speaking children and children who are blind and/or deaf who meet the inclusion criteria will be eligible for study participation if they are able to complete either the neurocognitive or behavioral assessments of the neuropsychological component and all other study procedures. Since retention in a cohort study is of central importance, numerous efforts will be employed to include in the cohort children with the highest likelihood of participation in the study for the long term. Also, children can be included in the study only if they and their parents/legal guardians are willing and able to provide informed consent and assent.

In summary, the following conditions comprise the inclusion criteria:

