#### 4.2.2 Exclusion Criteria

Among the children who fulfill the inclusion criteria, certain medical conditions and/or the inability to assess exposures of interest will deem them ineligible. Specifically, the following conditions comprise the exclusion criteria:

- Renal, other solid organ, bone marrow or stem cell transplantation
- Dialysis treatment within the past three months
- Cancer diagnosis or HIV diagnosis/treatment within last twelve months
- Current pregnancy or pregnancy within past twelve months
- Inability to complete major data collection procedures
- Current enrollment in a randomized clinical trial in which the specific treatment is unknown
- Not fluent in English or Spanish
- Plans to move out of area of any participating CKiD site (Families can be transferred to another CKiD site if they move)
- History of structural heart disease
- Genetic syndromes involving the central nervous system (e.g., Downs syndrome)
- History of severe to profound mental retardation (i.e., IQ<40, significant impairment in adaptive function and/or inability to independently execute selfcare skills)
- For cohort 3, children who are expected to receive renal replacement therapy within 6 months of date of enrollment will not be recruited.

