## 5.4 Follow-up Schedule

Approximately six hundred (600) children were enrolled over a four-year period in Cohort 1. In Cohort 2, approximately 300 children were enrolled over a two-year period. In Cohort 3, an additional 190 are expected to be enrolled. Participants enrolled in Cohort 2 followed the same contact pattern as Cohort 1. Participants were scheduled to return within 6 months of the baseline GFR assessment, depending on the age of the child and then annually for in-person follow-up visits for approximately 13 years in CKiD (i.e., through V15). Except for the GFR assessment, the neuro battery and some of the cardiovascular measurements, Cohort 3 will follow a similar contact pattern as the other cohorts. GFR assessment will be optional in cohort 3. These study visits are intended to be completed on an out-patient basis. In order to provide flexibility when scheduling study visits, each study visit may be scheduled during varying time periods. Specifically, V1a will be scheduled within one (1) year after the eligibility form is completed. V1b will be scheduled within 6 months but no more than one (1) year after V1a. The subsequent follow-up visits will be scheduled as follows:

- the first annual follow-up visit (V2) will occur one (1) year after V1a, plus or minus one month. However, if the visit is difficult to schedule, the visit can also be scheduled no more than two (2) years after V1a.
- Visit 3 will be scheduled two (2) years (± one month) after V1a or no more than three (3) years after V1a for visits that are difficult to schedule.
- Visit 4 will be scheduled three (3) years (± one month) after V1a or no more than four (4) years after V1a for visits that are difficult to schedule.

- Visit 5 will be scheduled four (4) years (± one month) after V1a or no more than five (5) years after V1a for visits that are difficult to schedule.
- Visit 6 will be scheduled five (5) years (± one month) after V1a or no more than six (6) years after V1a for visits that are difficult to schedule.
- Visit 7 will be scheduled six (6) years (± one month) after V1a or no more than seven (7) years after V1a for visits that are difficult to schedule.
- Visit 8 will be scheduled seven (7) years (± one month) after V1a or no more than eight (8) years after V1a for visits that are difficult to schedule.
- Visit 9 will be scheduled eight (8) years (± one month) after V1a or no more than nine (9) years after V1a for visits that are difficult to schedule.

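### Late entry at the baseline visit does not avoid survivorship bias for Cohort 3, whose eligibility rule screens out foreseen RRT in the first 6 months after enrollment

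*Protocol*

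**What the plan says.** Section 8.1.2 prefers disease duration to time on study as the axis for time-to-event analysis. It handles the period before recruitment by "incorporating the time from CKD onset until the date of the baseline visit as late entries to avoid survivorship bias", within a generalized gamma likelihood. Because many participants enter long after diagnosis, it adds that "we can restrict the analysis to the occurrence of RRT after 2 years from the CKD diagnosis". It wants further recruitment of children with glomerular disease and of very young children with non-glomerular disease to "inform the early portion of the survival curve proximate to CKD diagnosis".

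Eligibility for Cohort 3 (section 4.2.1) is a non-glomerular diagnosis "whose duration is less than 5 years at date of enrollment and age between 6 months to 16 years old". The exclusion list in section 4.2.2 then states: "For cohort 3, children who are expected to receive renal replacement therapy within 6 months of date of enrollment will not be recruited". Section 4.2.1 carries the same rule in its narrative. The clock for this rule is the date of enrollment, which the protocol does not tie to the baseline visit. Section 5.4 says only that "V1a will be scheduled within one (1) year after the eligibility form is completed".

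**The concern.** A left-truncated likelihood treats a child entering at duration t as representative of all children still event-free at t. Cohort 3 children meet a stricter test: they are event-free at t and are also judged unlikely to reach RRT in the next half-year. The likelihood in 8.1.2 represents the first condition and not the second. If risk time starts at baseline, follow-up inside the six-month window counts in the denominator, while the events most likely to fall there have been removed by selection. That is a form of the survivorship bias the sentence says it avoids.

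At stake is the shape of the early hazard since diagnosis. Cohort 3 enters within five years of onset, so the window falls mostly in the part of the curve that 8.1.2 wants to learn about.

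**Working it through.** **The plan's own Cohort 3 figure.** Section 9.1 sets the half-width of the 95% CI at p/2, so n = 1.96² × p(1−p)/(p/2)². For p = 5%, 7.5% and 10% this gives 291.95, 189.5 and 138.3, against 292, 190 and 138 in the protocol. The 190 is reproduced. It is a precision target; the protocol gives no RRT rate for Cohort 3.

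**Ceiling on affected person-time.** 190 × 0.5 y = 95 person-years. Without attrition this is 95/(190 × 4) = 95/760 = 12.5% of four years of follow-up, or 95/(190 × 2) = 95/380 = 25% of two years.

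**Where it falls on the duration axis.** Assume V1a on the enrollment date and entry uniform over 0–5 years. The share of Cohort 3 at-risk time at duration t that lies inside the window is min(0.5, t)/t:
- 0.5 y: 100%
- 1 y: 50%
- 2 y: 25%
- 3 y: 17%
- 5 y: 10%

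**Effect on the estimated hazard.** This was a left-truncated simulation with uniform entry, a constant true hazard of 0.03 per year, 5 years of follow-up and 3 million subjects per scenario. Children with RRT within 6 months of enrollment were dropped with probability 100%, 75% or 50% (the share foreseen). V1a was either on the enrollment date or uniform over the following 12 months. Entries are estimated/true hazard.

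| Foreseen | V1a lag | 0–1 y | 1–2 y | 2–3 y | 3–5 y | 0–5 y |
|---|---|---|---|---|---|---|
| 100% | none | 0.26 | 0.66 | 0.79 | 0.87 | 0.81 |
| 75% | none | 0.43 | 0.75 | 0.85 | 0.90 | 0.85 |
| 50% | none | 0.62 | 0.83 | 0.90 | 0.94 | 0.90 |
| 100% | 0–12 months | 0.49 | 0.85 | 0.93 | 0.96 | 0.94 |
| 75% | 0–12 months | 0.61 | 0.91 | 0.94 | 0.97 | 0.95 |
| 50% | 0–12 months | 0.76 | 0.95 | 0.97 | 0.98 | 0.97 |

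Beyond 5 years the ratio is 0.99 or higher. A hazard of 0.06 gives nearly the same values (0.80 to 0.97 for 0–5 y).

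**The two-year restriction.** With complete foresight and no lag, restricting to RRT after 2 years leaves 0.79 (2–3 y) and 0.87 (3–5 y). Children who enter between 1.5 and 5 years after diagnosis still carry window time past year 2.

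**Number of events.** Borrowing the planning rates of Table 9.2 (3, 6 and 9 per 100 person-years, not Cohort 3 rates), 190 × (1 − exp(−rate × 0.5)) = 2.8, 5.6 and 8.4 events in the window without the exclusion.

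**After the change.** Starting risk time 6 months after enrollment, with V1a at enrollment, returns ratios of 1.00 to 1.01 in all bands at both 100% and 75% foresight.

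**The case against.** Four counter-arguments carry weight.

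*Size.* The rule concerns foreseen RRT, so a reader might infer that the first six months are nearly event-free. The documents do not support that: unforeseen RRT can still occur, and part or all of the window can lapse before V1a. The 95 person-years are a ceiling. Cohort 3 is entirely non-glomerular and abnormal kidney function is optional for entry, so its RRT rate may be well below the planning rates.

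*Cohorts 1 and 2.* A reader might also infer that their person-time is unselected, so that delaying Cohort 3 makes the cohorts comparable. It is not unselected. Entry required two eGFR values of at least 30 (Cohort 1) or 45 (Cohort 2), and ESRD includes GFR below 15. At the fastest median decline in Table 9.1, 10.8 ml/min|1.73m² per year, going from 45 to 15 takes 30/10.8 = 2.8 years and from 30 to 15 takes 15/10.8 = 1.4 years. Cohort 1 used the older formula, which overestimates GFR. Rescaling its floor by 0.413/0.55 gives 22.5 and 7.5/10.8 = 0.7 year. For boys past their 13th birthday (k = 0.7) the floor becomes 17.7, about 0.25 year. These are illustrations from one subgroup, but the protection is often at least as long as six months. The comparability claim falls.

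*Source of the early curve.* Cohort 3 is not its only source. Section 8.1.2 also names children with glomerular disease, whom Cohort 3 does not enrol.

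*Status of the text.* Section 8.1.2 offers this as one approach and does not name Cohort 3; a risk-set start date could be left to an SAP. That softens the point. But the protocol itself names the entry time and the bias it is meant to avoid, and its own eligibility rule defeats that aim for one cohort.

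**Conclusion.** The point holds in a narrow form. Followed as written, the disease-duration analysis understates the Cohort 3 RRT hazard in the first 6 months after enrollment. The direction was the same in every scenario. Over the first five years of disease the Cohort 3 understatement ran from about 20% (complete foresight, V1a at enrollment) to about 3% (half foreseen, V1a up to a year later). It was largest in the first year of disease, and pooling the cohorts would dilute it.

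These sizes rest on assumptions outside the documents: uniform entry, constant hazard, five years of follow-up and the shares foreseen. The simulation also supposes that nobody is excluded by mistake. Children wrongly expected to need RRT within 6 months, who reach it soon afterwards, would leave some bias that a delayed start does not remove. Event counts are small. This is a cheap improvement to one analysis; it does not invalidate the time-to-event plan.

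**What to change.** In section 8.1.2, state that Cohort 3 children enter the RRT/ESRD risk set at the later of V1a and enrollment plus 6 months, with earlier person-time and events left out. Define the date of enrollment relative to V1a. Report the entry-at-baseline version as a sensitivity analysis.

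Cohorts 1 and 2 can keep entry at baseline, but the text should say that their eGFR floors also select against near-term ESRD. Cross-cohort comparisons of early hazard should be adjusted for or stratified by GFR at entry and read with that limitation. Iohexol GFR is optional in Cohort 3, so this would rest on estimated GFR from the V1a serum creatinine and cystatin C.

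The cost is a few sentences and one changed entry date in the code, with a loss of up to 95 person-years and of any unforeseen RRT inside the window. The sensitivity analysis retains those data.

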# 8.1.3 Analytic Method of Nested Studies

It is expected that numerous hypotheses about pathogenesis of kidney disease will be investigated within the study. Many of these hypotheses will involve highly technical, and, in some cases, expensive and time-consuming laboratory assays. For this reason, and because the study populations will often be very specific, it will not be possible to investigate these scientific questions in the full cohort. To make efficient and scientifically meaningful comparisons in such situations, it will often be necessary to either: 1) identify cases and match them to controls based upon specific characteristics to perform nested case-control analysis, or 2) select a sub-cohort in which to perform a case-cohort analysis.

KIDMAC will provide essential design and analytic support to these projects to ensure that the scientific questions can be addressed and that appropriate inferences are drawn from the data. These activities require not only epidemiological and statistical expertise, but rely upon the proposed leadership of KIDMAC in the area of study coordination as it relates to the efficient tracking and accessing of samples from the national repository. In nested case-control studies, we will make extensive use of conditional logistic regression for determining factors associated with case status in the study pathogenesis studies. We will ensure that matching is done according to appropriate epidemiologic principles such that potential controls for each case have been followed for at least as long as the case, to ensure that they had equal opportunity to develop the outcome that determines case status. In case cohort analyses, we will use a weighted estimating equations approach [Barlow 1999].

# 8.2 Examples of Aim-Specific Analyses

Below, we describe specific analyses for examining the associations of decline in kidney function on the levels of and changes in biomarkers for specific aims related to neurocognitive development, cardiovascular disease, and growth.

# 8.2.1 Intelligence Quotient

The intelligence quotient (IQ) is a general and stable indicator of general cognitive functioning that will be validly and reliably measured on children 30 months and older in CKiD. Let  $Y_{ij}$  be the IQ as derived from the WPPSI-III for children aged 30 months to 5 years, or the WASI for children aged 6 to 18 years for child i at visit j, where visit j is taken at time t.

A regression of the form  $Y_{ij} = b_0 + b_1t_{ij} + b_2G_{ij} + b_3G_{ij}t_{ij}$ , where the variable  $G_{ij}$  is the decline of GFR in the preceding year scaled to a 5-unit difference (= (GFRij-1 – GFRij)/5), will describe the trajectory of cognitive functioning as a line with intercepts  $b_0$  for those with no GFR decline and  $b_0 + b_2$  for those with a 5 ml/min|1.73m^2 decline in GFR, and slopes  $b_1$  for individuals who have no GFR decline and  $b_1 + b_3$  for those with a 5 ml/min|1.73m^2 decline in GFR. Here, the intercepts describe the initial difference in IQ due to decline in GFR, and the slopes describe the linear rate of change in IQ due to decline in GFR. Since this study is planning to measure GFR every two years, we will CKiD Protocol 91 06/01/16 to 08/01/17 OSMB Approved

either annualize the change in GFR over the preceding two years for which the observed data will be available or we will estimate the GFR not measured directly in a given year using the serum creatinine which will be available every year. Specifications other than the annual difference in GFR will be explored. Also, we will be able to investigate nonlinear changes in IQ over time by a polynomial expansion of tij into say the cubic function  $t_{ij} + t^{2}_{ij} + t^{3}_{ij}$ . The intrinsic statistical dependence of repeated IQ measurements taken on individuals will either be included as additional parameters using mixed effects models or will be treated as a nuisance using generalized estimating equations.

The above regression will be extended to control for possible confounding by age since diagnosis and socioeconomic status by the addition of  $b_4A_{ij}$  and  $b_5SES_{ij}$ , where  $A_{ij}$  is the percent of a child's age that the child has lived with CKD centered about 50% (= [100(t - age of diagnosis of CKD) / t ] - 50) and SESij is the socioeconomic status measured by family income and/or parental educational achievement (For more detail regarding the specification of Age please see section 8.2.1). Here  $b_4$  is quantifies the shift of the regression line for a one percent increase in age since CKD diagnosis. The parameter  $b_5$  quantifies the effect of a 1-unit increase socioeconomic status on the shift of the regression line. In this extended model, the slope  $b_1 + b_3$  estimates the effect of a decline of 5 ml/min|1.73m^2 of GFR, independent of age at diagnosis and socioeconomic status. To explore potential effect modification, the above extended model will be stratified by the presence of psychiatric diagnoses (e.g. ADHD).

In addition to general cognitive functioning as measured by IQ, the Neurocognitive Subcommittee is interested in exploring overall achievement, adaptive and social behavior, and measures of attention.

